Sustainable East Africa Research in Community Health
(SEARCH) Collaboration

**Statistical Analysis Plan for Health Outcomes
in Phase 1 of the SEARCH-IPT Study**

[name], PhD¹
[name], MS¹
[name], MD²
[name], MD²

November 10, 2021
Version 2.1

¹University of Massachusetts, Amherst; ²University of California, San Francisco

Contents

1	Brief study overview	2
2	Primary outcome: IPT uptake	4
3	Secondary outcome: HIV-associated TB incidence	7
4	Secondary outcome: Knowledge, attitudes, and practices regarding IPT	8
5	Secondary outcome: IPT completion among persons starting IPT	9
6	Appendix	11
6.1	History of changes:	11
6.2	Select survey questions:	11
6.3	Power calculations:	12

1 Brief study overview

The SEARCH-IPT Study is a cluster randomized trial designed to evaluate whether a multicomponent intervention increases uptake of isoniazid (INH) preventive therapy (IPT) and reduces the incidence of tuberculosis (TB) in Uganda (Clinicaltrials.gov: NCT03315962). Details of the multiphase trial design and procedures can be found in the Study Protocol. Here, we provide the statistical analysis plan for health outcomes in Phase 1 of the study. Analysis plans for qualitative outcomes, cost-effectiveness outcomes, and business outcomes are available elsewhere. A history of changes to this analysis plan is given in the Appendix.

Study design: Phase 1 of the SEARCH-IPT Study aims to increase provider prescription and patient use of IPT among adults in HIV care in Uganda. Within the Eastern, East-Central, and Southwestern regions of Uganda, districts were first grouped into 14 clusters of 4-7 districts. To improve statistical power [1, 2], these groups were pair-matched on characteristics expected to be predictive of IPT uptake: region, number of adults in active HIV care, urbanicity, and presence of a SEARCH universal HIV “test and treat” trial site. Within each pair, the groups were then randomized to intervention or the standard-of-care. There are 7 groups in each arm. Formal power calculations are given in the Appendix.

Study arms: In districts randomized to the intervention, the groups are the mini-collaboratives

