We will focus on effect measures on the absolute scale and for the N districts with both baseline and follow-up data. Primary analyses will focus on the change from baseline to year-1. Secondary analyses will focus on change from baseline to year-2 and from year-1 to year-2. We will report point estimates and two-sided 95% confidence intervals for the arm-specific annual responses, the arm-specific estimates of change, and the effect estimates. Primary analyses will weigh the N districts equally and include all districts, including those created during follow-up. We will use the same approach to statistical inference as the primary endpoint.

Additional analyses: We will repeat the above analyses stratifying on whether the respondent is a DHO or a DTLSS.

5 Secondary outcome: IPT completion among persons starting IPT

A key intermediate between IPT uptake and TB prevention is IPT completion. Therefore, we will also assess the SEARCH-IPT intervention on “IPT completion”, defined as dispensation of a full course of IPT within 9 months of initiation. As detailed in the corresponding SOP, this endpoint will be measured among $N = 800$ (400 persons/arm) who are aged 15+ years, HIV-infected, and started IPT at one of 16 facilities in Southwestern region. Within each clinic, these participants will be sampled such that half initiated IPT before Q3-2019 and half initiated in Q3-2019 (during the “100-day IPT push”).

Data source: For each sampled participant, de-identified data on IPT completion (via INH pills dispensed over 9 months) will be obtained from the IPT register and blue cards. Additionally, data on the following variables will be recorded: gender, date of birth, marital status, ARV regimen, ARV switches while on IPT (date and new regimen), most recent HIV RNA viral load, if on Septrin or Dapsone while taking INH, and diagnosis of active TB.

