Effect estimation: When evaluating IPT completion among the subsample of initiators, we will evaluate the arm-specific and relative risk of IPT completion with an individual-level TMLE, adjusting for sex, age, and timing of IPT initiation. The details of this approach are given in van der Laan et al. [16]. In brief, this approach assumes the adjustment covariates are sufficient to “block” the impact of shared factors that may differ between clusters, here clinics. In other words, two participants from two different clinics would have the same outcome probability if they had the same gender, age, and IPT initiation date *and* their respective clinics had received the same level of the treatment. This approach also relies on the assumption that sampled participants are conditionally independent, given the treatment assignment and the adjustment set. These assumptions are reasonable given that, beyond the intervention, the major driver of IPT prescribing practices and, thus, completion are secular factors (e.g., the Q3-2019 “100-day IPT push”) and the participant’s timing of IPT initiation is included in the adjustment set.

To flexibly control for sex, age, and timing of IPT initiation, we will implement TMLE with Super Learner, an ensemble machine learning algorithm that creates the best weighted combination of predictions from a set of candidate learners [17]. Our candidates will include multivariate adaptive regression splines, main terms logistic regression, and the simple mean. In sensitivity analyses, we will implement TMLE using main terms logistic regression instead of Super Learner. Additional sensitivity analyses will include marital status in the adjustment set and include penalized regression in the Super Learner library.

We will also evaluate IPT completion using an analogous analysis as for the primary endpoint. Specifically, treating the clinic as the independent unit, we will use adaptive pre-specification to select among the following individual-level adjustment variables the ones that maximize precision in TMLE: sex, age, and timing of IPT initiation [5, 18]. We will also report unadjusted estimates from this approach as well as conduct an analysis weighting proportionally to the clinic’s total IPT starts and an analysis treating clinics as fixed effects.

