For all approaches, we will test the *null hypothesis* of no improvement from the intervention with a one-sided test at the 5% significance level. We will also report point estimates and two-sided 95% confidence intervals for the relative effect, the absolute effect, and the arm-specific mean outcomes. We will also report total completions by arm.

Additional analyses: We will repeat the above analyses within subgroups defined by sex, timing of IPT initiation (before Q3-2019 “100-day IPT push” or during Q3-2019), age group (15-24 years or 25+ years), and marital status (never married, married/living together, divorced/separated/widowed, missing). We will also use an individual-level TMLE to examine predictors of non-completion. We will provide descriptive statistics on the subsample, including their demographics and care outcome (e.g., ARV switches).

Secondary endpoint: We will repeat the above analyses to examine the effect of the SEARCH-IPT intervention on viral suppression, defined as HIV RNA viral level <400 copies/mL.

6 Appendix

6.1 History of changes:

- Version 1.0 was locked on July 18, 2021 prior to unblinding and effect estimation for IPT uptake (the primary outcome), IPT completion among persons starting IPT, and HIV-associated TB incidence.
- Version 2.0 was created to include the pre-specified analysis plan for the quantitative surveys on knowledge, attitudes, and practices regarding IPT. Version 2.0 was locked on September 15, 2021, prior to unblinding and effect estimator for the survey outcomes.
- Version 2.1, this version, was created to correct grammatical errors and other typos. Version 2.1 was locked on November 10, 2021 prior to submission of the manuscript.

6.2 Select survey questions:

[figure not shown]
The following are examples of survey questions, designed to understand the impact of the SEARCH-IPT intervention on IPT knowledge, attitudes, and practices among DHOs and DTLSSs. Full survey materials are available elsewhere.

1. How familiar are you with IPT? With responses: 1: no knowledge of IPT; 2: somewhat unfamiliar – low knowledge of IPT; 3: somewhat familiar; 4: familiar; 5: very familiar – high knowledge of IPT.
2. How strong is the evidence that INH prevents active TB in HIV-infected patients? With responses: 1: very weak; 2: weak; 3: mixed; 4: strong; 5: very strong.

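### The completion analysis with clinics as fixed effects cannot deliver the test of the intervention effect that the SAP asks of it, because every clinic lies wholly in one arm

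*SAP*

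**What the plan says.** SAP section 1 describes groups of 4–7 districts formed into matched pairs: "Within each pair, the groups were then randomized to intervention or the standard-of-care". SAP section 5 samples 800 patients, 400 per arm, who "started IPT at one of 16 facilities in Southwestern region", chosen within each clinic so that "half initiated IPT before Q3-2019 and half initiated in Q3-2019". The same section treats arm as a property of the clinic when it compares patients on the condition that "their respective clinics had received the same level of the treatment".

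The lead completion analysis is an individual-level TMLE. A second analysis takes the clinic as the independent unit. To this the SAP adds unadjusted estimates, an analysis weighted by IPT starts, and "an analysis treating clinics as fixed effects". For this last item it gives no model equation, constraint, estimand or variance.

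The next paragraph covers all approaches. Each is to test the null of no improvement from the intervention "with a one-sided test at the 5% significance level" and to report "two-sided 95% confidence intervals for the relative effect, the absolute effect, and the arm-specific mean outcomes". The same analyses are then repeated in four sets of subgroups and for viral suppression.

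**The concern.** A fixed-effects analysis removes all differences between clinics and estimates what varies within them. Arm does not vary within a clinic, so removing clinic differences removes the arm contrast too. The analyst must then either accept whichever column the software drops or choose a definition after the SAP is locked.

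The looser reading, conditioning on the 16 clinics as given, yields a number, but its interval reflects only patient-to-patient variation inside clinics. The lead individual-level TMLE also assumes patients are conditionally independent given arm, sex, age and timing of initiation. If the two agreed, that could look like support from a second method, although both leave out residual between-clinic variation.

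**Working it through.** **Inputs from the documents.** 16 clinics, 800 patients, 400 per arm, one-sided 5% test (SAP section 5). Control completion 44%, range 30–50%, and matched-pair k_m = 0.2 for DHO groups (protocol section 6.5.2.1). An alternative k = 0.25, given for IPT uptake (SAP section 6.3).

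**Assumptions.** 8 clinics per arm (16/2); 50 patients per clinic (800/16); independent clinics; a between-clinic CV k for completion, which the documents do not give.

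**Step 1: the plan's own figure.** The protocol states at least 80% power for a 40% relative increase (0.44 to 0.616) with 12 groups per arm and 30–40 patients per group. The matched formula for proportions is

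power = Φ( √[(c − 2)(p1 − p0)² / (p0q0/m + p1q1/m + k²(p0² + p1²))] − 1.96 ).

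With c = 12 and m = 30:
- Denominator: 0.00821 + 0.00788 + 0.02292 = 0.03902.
- Numerator: 10 × 0.176² = 0.30976.
- √7.94 = 2.818, so power = Φ(0.858) = 0.804.

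With m = 40, power is 0.845. The stated figure reproduces, so k_m = 0.2 is the planning value, but it describes matched DHO groups and not clinics.

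**Step 2: clinic indicators plus arm.** The arm column equals the sum of the intervention clinics' indicators.
- 16 indicators + arm: 17 columns, rank 16. Arm is aliased.
- Adding initiation period: 18 columns, rank 17. Arm is still aliased.
- Sex and age add columns of their own but leave the identity between arm and the clinic indicators intact.
- Replacing arm by arm × period gives 18 columns of rank 18, but that asks whether the effect differs between periods, not whether there is one.

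This step needs no assumption about completion, CV or clinic size.

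**Step 3: conditional reading.** Take the difference between the average clinic proportions of the two arms, with a standard error from within-clinic variance only. Let B = (kp)² be the between-clinic variance and W = (p(1 − p) − B)/50 the within-clinic variance of a clinic proportion. With no intervention effect, the true one-sided error is 1 − Φ(1.645 × √[W/(W + B)]).

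At p = 0.44 and k = 0.2:
- B = 0.088² = 0.00774 and W = (0.2464 − 0.00774)/50 = 0.00477.
- √(0.00477/0.01252) = 0.618, so the standard error is too small by a factor of 1/0.618 = 1.62.
- Error = 1 − Φ(1.016) = 0.155.

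The design-effect version gives nearly the same. ICC = 0.00774/0.2464 = 0.031, design effect = 1 + 49 × 0.0314 = 2.54, and error = 1 − Φ(1.645/1.594) = 0.151.

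Beta-binomial simulation, 100,000 replicates per row:

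| Completion | CV | Error, formula | Error, simulated | 95% interval coverage |
|---|---|---|---|---|
| 44% | 0 | 0.050 | 0.049 | 95% |
| 44% | 0.10 | 0.082 | 0.082 | 90% |
| 44% | 0.20 | 0.155 | 0.156 | 78% |
| 44% | 0.25 | 0.192 | 0.196 | 70% |
| 30% | 0.20 | 0.115 | 0.115 | 85% |
| 30% | 0.25 | 0.143 | 0.143 | 80% |
| 50% | 0.20 | 0.174 | 0.175 | 74% |
| 50% | 0.25 | 0.215 | 0.215 | 65% |

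**Step 4: comparison.** In the same simulations a clinic-level t-test with 14 degrees of freedom has error 0.049 to 0.051 in the tabulated scenarios. That holds only while clinics are independent of one another.

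**The case against.** The SAP never writes down a dummy-variable regression. The phrase sits in a paragraph on clinic-level TMLE. With clinics nested in arm, the contrast of average clinic means is a plain function of the 16 clinic means and can be computed, as can the arm means. A reader might infer that no version of the analysis can yield an arm contrast. The documents do not support that; non-estimability belongs to the model with clinic indicators. It also stands that conditional inference has its nominal error for a null about the mean difference between these 16 particular clinics. That null is not the one the SAP sets, which concerns improvement due to the intervention. Each clinic was seen under one arm only, so clinic differences stay mixed with arm.

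A reader might also infer that the error rate is simply three times nominal. That describes one scenario: 44% completion and CV 0.2. The CV is borrowed from matched DHO groups in a design with 12 groups per arm, and the split of clinics and patients is assumed. At CV 0.1 the error is about 8%, and with no clinic variation it is nominal.

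Nor does the SAP say that this analysis will be presented as confirming the completion result. It is listed last among the analyses accompanying the clinic-as-unit approach, which is itself planned.

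**Conclusion.** The point holds as a defect of this one analysis. Under the clinic-indicator reading, the arm effect the SAP requires does not exist as an estimable quantity; this follows from the design alone. Under the conditional reading, the test and intervals do not address the stated null. Their one-sided error is then about 12–22% over 30–50% completion and CV 0.2–0.25, which is 2.3 to 4.3 times nominal, and it falls to 5% as clinic variation vanishes. These figures rest on 8 clinics per arm, 50 patients per clinic, independent clinics and a CV that the documents do not supply at clinic level.

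The consequence is limited: the analysis is supplementary, the outcome is secondary, and neither the primary endpoint nor the clinic-as-unit analysis depends on it.

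**What to change.** Delete the fixed-effects item from SAP section 5. Alternatively, keep it with its model written out, labelled as a description of these 16 clinics, and exempt it from the one-sided test and the intervals for the intervention effect. The exemption should extend to the subgroup and viral-suppression repeats. Cluster-level inference on completion should rest on the clinic-as-unit analysis already planned. Replacing the item with a clinic random-intercept model would add little, since it largely duplicates that analysis.

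Add one sentence on a limit that remains. According to protocol section 9.2.1, the Southwestern region contains 2 intervention and 2 control groups, so the 16 clinics sit in four randomized groups. Correlation within those groups is not captured when the clinic is the unit, although protocol section 6.5.2.1 promises to account for clustering by randomization group.

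The cost is one or two lines of SAP wording and no new data. Version 1.0 was locked before unblinding of completion and version 2.1 before manuscript submission, so the change should be a documented amendment. Its reason lies in the design and not in any result.
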